## 12.0 STATISTICAL CONSIDERATIONS

### 12.1 Study Design/Endpoints

This is a phase I, dose escalation study of cabozantinib for advanced solid tumors in persons with HIV infection. The primary endpoint of the study is the safety and tolerability of single agent cabozantinib and to determine the maximal tolerated dose (MTD) in this participant population. The study will be a standard phase I dose escalation trial with a 3+3 design. The study agent will be administered continuously in 28 day cycles.

Participants will be stratified based on HAART with the currently recommended dosing regimen. Participants on ritonavir or cobicistat (potent CYP3A4 inhibitor)-containing HAART will be on Stratum A; participants on efavirenz or etravirine (CYP3A4 inducer)-containing HAART will be on Stratum B, and all other participants (including those without antiretroviral therapy) will be on Stratum C. Dose escalation and MTD determination will be done for each stratum individually. Participants are considered evaluable for the purpose of cohort dose escalations if in the first cycle they either experience a dose-limiting toxicity (DLT) (see below), or receive at least 80% of the planned treatment dose and are followed for one full cycle without a DLT. Participants receiving less than 80% of the treatment dose during cycle 1 without a DLT may be replaced for the purpose of safety and PK evaluation at the discretion of the study team.

Dose escalation decisions for cabozantinib will be made after evaluation of toxicities in the first cycle of therapy. In this trial, a dose-limiting toxicity (DLT) will be defined as any cabozantinib-related grade 3 or 4 non-hematologic toxicity during the first cycle of therapy, including grade 3 nausea and/or vomiting and grade 3 diarrhea despite prophylaxis and/or treatment or any of the following grade 4 hematologic toxicities during the first cycle of therapy: thrombocytopenia and neutropenia of any duration (with or without fever or documented infection); additionally, treatment delay of greater than 7 days during Cycle 1 due to unresolved toxicity or any dose reduction required during Cycle 1 due to a cabozantinib-related adverse event will be considered a DLT. If a DLT occurs in one participant at a particular dose level, up to 3 additional participants will be added to that cohort. If a second participant experiences a DLT, the maximally tolerated dose (MTD) of the study will have been exceeded. If 2 DLTs are experienced at the first cohort, dose de-escalation cohorts (up to Dose Level -1 for Stratum A; up to Dose Level -2 in Stratum B and Stratum C) will be permitted according to the study schema suggested in the treatment plan.

### 12.2 Sample Size/Accrual Rate

No formal statistical hypothesis testing is planned for the primary analysis. Sample size estimates are in agreement with those of a traditional phase I dose escalation 3+3 design. It is expected that the study will enroll approximately 16 to 42 participants across potentially three Strata (Ritonavir or Cobicistat (CYP3A4 inhibitor)-containing HAART [**Stratum A**]; Efavirenz or Etravirine (CYP3A4 inducer)-containing HAART [**Stratum B**]; and Others [**Stratum C**]). Among the expected 16 to 42 enrolled participants, 4 to 18 are expected to be enrolled in Stratum A, 6 to 18 are expected to be enrolled in Stratum B, and 6 participants are expected to be enrolled in Stratum C.

Following the determination of the MTD in each stratum, the MTD dose level for each stratum may be expanded to 6 to 12 participants according to participant availability for further characterization of toxicity, preliminary assessment of response and additional translational study samples. A decision to halt accrual because of lack of participant availability will be at the discretion of CTEP investigators.

The estimated accrual rate for this study is 1 - 2 participants/month.

### **12.3 Stratification Factors**

Participants will be stratified based on HAART with the currently recommended dosing regimen. Participants on ritonavir or cobicistat (CYP3A4 inhibitor)-containing HAART will be on Stratum A; participants on efavirenz or etravirine (CYP3A4 inducer)-containing HAART will be on Stratum B, and all other participants (including those without antiretroviral therapy) will be on Stratum C. Dose escalation and MTD determination will be done for each stratum individually.

### **12.4 Analysis of Secondary Endpoints**

Secondary endpoints for this study include response rates and effects of therapy on HIV viral load and CD4+ and CD8+ cell counts, as well as the results of pharmacokinetic studies. For participants with measurable disease, response evaluations will occur at 2 cycle intervals via RECIST 1.1. Study treatment may continue indefinitely until one of the following criteria applies: 1) unacceptable toxicity (including DLT in cycle 1); 2) progressive disease; or 3) participant withdrawal or removal.

To investigate possible pharmacokinetic interactions between cabozantinib and antiretroviral therapy in persons with HIV infection, pharmacokinetic analysis calculations will be conducted using WinNonlin (Pharsight Corporation, Mountain View, CA) with noncompartmental or compartmental methods. Relevant pharmacokinetic parameters will be computed for cabozantinib and relevant metabolites. The pharmacokinetic variables will be tabulated and descriptive statistics (e.g., geometric means and coefficients of variation) calculated for each dose level. Pharmacokinetic parameters (i.e.,  $T_{1/2}$ , Cl, and AUC) will be compared across relevant antiretroviral therapies using nonparametric statistical testing techniques. Concentrations obtained from the time of disease progression and the time of a DLT or other persistent and severe toxicity will be treated as independent samples and summarized in a descriptive manner. Correlations with toxicity and efficacy will be assessed using nonparametric statistical testing techniques. Significance for comparisons will be at the  $p<0.05$  level.

To investigate the effects of cabozantinib on participant immune status and HIV viral load, trends in CD4+ and CD8+ counts and viral load determinations during trial participation will be evaluated. A repeated measures analysis of variance will be used to assess the effect of cabozantinib on CD4+ and CD8+ cell counts and HIV viral loads across time points. Analyses will be done per stratum, where the data are sufficient. If the data do not meet the assumptions of normality, Friedman's test, the nonparametric analogue to a repeated measures analysis of variance, will be used.

Collectively and over each stratum, binomial proportions and their 95% confidence intervals will be used to preliminarily assess response rates for single agent cabozantinib in malignancies for which at least 4 participants have been enrolled.

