## PROTOCOL SYNOPSIS

**Title:** Phase I Trial of Cabozantinib (XL184) for Advanced Solid Tumors in Persons with HIV Infection

**Phase of Study:** Phase I

**Participating Institutions:** This protocol will be open to all AMC member sites.

**Accrual Target:** 16 to 42 participants

**Population:** Participants with incurable recurrent or metastatic solid tumors and HIV infection.

**Regimen:** This is a phase I, dose escalation study of cabozantinib (XL184) for advanced solid tumors in persons with HIV infection. Cabozantinib will be administered orally as a once daily dose continuously for 28-day cycles, according to the Protocol Schema. Participants will be stratified into three groups based on which HAART therapy they are receiving. The first group (**Stratum A**) will be participants on either ritonavir or cobicistat (potent CYP3A4 inhibitor)-containing antiretroviral therapy. Since a potential interaction leading to higher drug levels of cabozantinib in participants on ritonavir or cobicistat is expected, participants will be dose escalated, starting at ~33% of the standard dose (60 mg), using a classic 3 + 3 phase I clinical trial design. Dose increases will be in 20 mg increments to a maximum of 60 mg/day. The second group (**Stratum B**) will be participants being treated with either efavirenz or etravirine-containing regimens, in whom CYP3A4 induction may lead to lower levels of the study drug. These participants will be treated at the standard dose of cabozantinib, then dose escalated by 20 mg/cohort to a maximum of 100 mg/day in a 3 + 3 design. The third group (**Stratum C**) will include participants taking antiretrovirals not specified in Stratum A or B, or who are not receiving active antiretroviral therapy. These participants will be treated at the standard dose of 60 mg/day; no dose escalation is planned in this Stratum.

In this trial, a dose-limiting toxicity (DLT) will be defined as any cabozantinib-related grade 3 or 4 non-hematologic toxicity during the first cycle of therapy, including grade 3 nausea and/or vomiting and grade 3 diarrhea despite prophylaxis and/or treatment or any of the following grade 4 hematologic toxicities during the first cycle of therapy: thrombocytopenia, neutropenia of more than 5 days duration, and neutropenia of any duration with fever or documented infection; additionally, treatment delay of 14 days or greater during Cycle 1 due to unresolved toxicity or any

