dose reduction required during Cycle 1 due to a cabozantinib-related adverse event will be considered a DLT.

All participating participants will have pharmacokinetic sampling studies. Response evaluation by RECIST 1.1 will be obtained on all participants at baseline and at 8 week intervals.

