**Duration:**

Treatment may continue indefinitely until one of the following criteria applies: 1) unacceptable toxicity (including DLT in cycle 1); 2) progressive disease; or 3) participant withdrawal or removal.

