### 5.2 Definition of Dose-Limiting Toxicity

Dose escalation decisions for cabozantinib will be made after evaluation of toxicities in the first cycle of therapy. In this trial, a dose-limiting toxicity (DLT) will be defined as any cabozantinib-related grade 3 or 4 non-hematologic toxicity during the first cycle of therapy, including grade 3 nausea and/or vomiting and grade 3 diarrhea despite prophylaxis and/or treatment or any of the following grade 4 hematologic toxicities during the first cycle of therapy: thrombocytopenia and neutropenia of any duration (with or without fever or documented infection); additionally, treatment delay of greater than 7 days during Cycle 1 due to unresolved toxicity or any dose reduction required during Cycle 1 due to a cabozantinib-related adverse event (including for intolerable cabozantinib-related grade 2 non-hematological toxicity – per Table 6-1) will be considered a DLT.

For all participants who experience a DLT or other persistent and severe toxicity, a blood sample for pharmacokinetics analysis will be requested from the participant (if feasible). The samples should be drawn as close as possible to the time of the event.

If a DLT occurs in one participant at a particular dose level, up to 3 additional participants will be added to that cohort. If a second participant experiences a DLT, the maximally tolerated dose (MTD) of the study will have been exceeded. If 2 DLTs are experienced at the first cohort, one dose level de-escalation (Dose Level -1) will be permitted according to the study schema suggested in the treatment plan.

Management and dose modifications associated with the above adverse events are outlined in [Section 6.0](#).

Dose escalation will proceed in participant cohorts within each Stratum ([Section 5.1](#)) according to the following scheme. Participants are considered evaluable for the purpose of cohort dose escalations if in the first cycle they either experience a DLT (defined above), or receive at least 80% of the planned treatment dose and are followed for one full cycle without a DLT. Participants receiving less than 80% of the treatment dose during cycle 1 without a DLT may be replaced for the purpose of safety and PK evaluation at the discretion of the study team.

Number of Participants with DLT at a Given Dose Level	Escalation Decision Rule
0 out of 3	Enter 3 participants at the next dose level.

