#### **5.4 Duration of Therapy**

In the absence of treatment delays due to adverse event(s), treatment may continue until one of the following criteria applies:

- Disease progression,
- Intercurrent illness that prevents further administration of treatment,
- Dose-limiting toxicity (DLT requiring discontinuation of therapy, as defined in [Section 5.2](#)). Dose reductions in the first cycle of therapy for cabozantinib-related adverse events are permitted.
- Other unacceptable adverse event(s),
- Treatment delay of 14 days or greater during Cycle 1 due to unresolved toxicity (DLT definition, [Section 5.2](#)).
- Treatment delay in subsequent cycles > 6 weeks due to toxicity (treatment delays for other reasons may be permitted at the discretion of the Study Chairs),
- Participant decides to withdraw from the study.
- General or specific changes in the participant's condition render the participant unacceptable for further treatment in the judgment of the investigator, including:
  - Necessity for treatment with other anticancer treatment prohibited by the protocol.
  - Change to a ritonavir or cobicistat-containing antiretroviral regimen for a participant enrolled on a different study arm (see [Section 5.3.1.2](#)).
  - Sexually active participants who refuse to use medically accepted barrier methods of contraception (e.g., male condom, female condom) during the course of the study and for 6 months following discontinuation of study treatment.
  - Women who become pregnant or are breastfeeding.
- Request by regulatory agencies for termination of treatment of an individual participant or all participants under the protocol.
- Significant noncompliance with the protocol schedule in the opinion of the investigator.
- The minimum dose of study treatment for Stratum A will be the Dose Level -1 dose, and the lowest dose of study treatment for Stratum B and Stratum C will be the Dose Level -2 dose. Participants who cannot tolerate the lowest Dose Level dose for the specified study Stratum will have study treatment discontinued.

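### Section 12.4 and the synopsis stop treatment at any Cycle 1 DLT, while Sections 5.4 and 6 keep many of the same participants on drug

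*Combined protocol and SAP*

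**What the plan says.** **Stopping rules.** Section 12.4: "Study treatment may continue indefinitely until one of the following criteria applies: 1) unacceptable toxicity (including DLT in cycle 1". The synopsis, under Duration, uses the same phrase: "unacceptable toxicity (including DLT in cycle 1". Neither limits it to some DLTs. Section 5.4 stops for a DLT requiring discontinuation, refers to Section 5.2 for the definition, and adds: "Dose reductions in the first cycle of therapy for cabozantinib-related adverse events are permitted". It has a separate bullet: "Treatment delay of 14 days or greater during Cycle 1 due to unresolved toxicity", labelled as the Section 5.2 DLT definition. Section 5.6 makes the Section 5.4 list the basis for removal. Section 6.0 states in bold that Cycle 1 dose modification will be allowed, with therapy continuing unless another discontinuation criterion applies.

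**DLT definitions.** Section 5.2 includes "treatment delay of greater than 7 days during Cycle 1 due to unresolved toxicity or any dose reduction required during Cycle 1". Section 12.1 likewise: "any dose reduction required during Cycle 1 due to a cabozantinib-related adverse event will be considered a DLT". The synopsis agrees on reductions ("dose reduction required during Cycle 1 due to a cabozantinib-related adverse event will be considered a DLT") but sets the delay at "treatment delay of 14 days or greater during Cycle 1 due to unresolved toxicity". It counts Grade 4 neutropenia only when it lasts more than 5 days or comes with fever or documented infection; Sections 5.2 and 12.1 count it at any duration.

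**Dose modification.** Tables 6-1 and 6-2 and Section 6.1.4 set out resumption after several events that are DLTs if they occur in Cycle 1.

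**The concern.** An investigator whose participant has a Cycle 1 DLT finds two instructions. Section 12.4 and the synopsis say treatment ends. Sections 5.4 and 6 say that in many cases it continues, usually at a lower dose. The protocol is open to all member sites, so the same event could be handled differently from one site to the next.

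At stake is whether a participant with incurable cancer who could tolerate a lower dose stays on drug, and whether that participant contributes later response, safety, CD4/CD8 and viral-load data. The differing synopsis definition is a further problem: it bears on what counts as a DLT in the first place.

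**Working it through.** There is no stated figure to reproduce. The check sets the rules side by side for each Cycle 1 event.

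| Cycle 1 event | DLT under 5.2/12.1 | DLT under synopsis | Under 12.4 / synopsis | Under 5.4 / Section 6 |
|---|---|---|---|---|
| Dose reduction for a related event | Yes | Yes | Stop | Continue at reduced dose (5.4, 6.0) |
| Related Grade 3 non-hematologic event | Yes | Yes | Stop | Interrupt; may resume at the same or a lower dose, depending on the Table 6-1 row |
| Related Grade 3-4 asymptomatic lipase/amylase elevation | Yes | Yes | Stop | May continue or restart (6.1.4) |
| Grade 4 thrombocytopenia | Yes | Yes | Stop | Resume one level lower (Table 6-2) |
| Grade 4 neutropenia | Yes, any duration | Only if over 5 days, or with fever or infection | Stop where it is a DLT | Resume one level lower (Table 6-2) |
| Toxicity hold of more than 7 and under 14 days (8-13 whole days) | Yes | No | Stop under 12.4; no stop under the synopsis | Continue |
| Toxicity hold of 14 days or more | Yes | Yes | Stop | Stop |
| Related Grade 4 non-hematologic event, general rule | Yes | Yes | Stop | Stop, with a clinical-benefit exception needing Study Chair approval (Table 6-1) |

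The first six rows conflict, the sixth only when Section 12.4 is read with 5.2/12.1. The seventh agrees throughout. The eighth agrees apart from its exception.

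**Cross-references.** Section 5.4 sends the reader to Section 5.2 for the DLTs that require discontinuation, but Section 5.2 does not identify them; the actions are in Section 6. Section 5.4 also labels the 14-day rule as the Section 5.2 DLT definition, whereas Section 5.2 says more than 7 days.

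**Synopsis neutropenia.** The practical gap is narrower than the wording. Table 6-2 directs a one-level reduction after any Grade 4 neutropenia, so if dosing resumes within Cycle 1 for a related event, the synopsis's own dose-reduction clause makes it a DLT. The gap remains when dosing resumes later.

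**Data lost.** Suppose a participant with measurable disease stops on Day 10.
- The off-treatment CT is due within 7 days: 10 + 7 = Day 17.
- The on-treatment CT after two cycles falls at 2 × 28 = Day 56 and is not done.
- CD4/CD8 and viral load are taken at discontinuation, but the Day 22 and 12-week on-treatment values are lost.
- Safety follow-up runs 30 days, to 10 + 30 = Day 40, or longer if toxicity is unresolved.
- PK is only partly affected: a sample is requested at DLT, and the steady-state collection can be rescheduled or waived.

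**How often.** The documents give no DLT rate. Assuming 10%, 20% or 30%, the chance of at least one Cycle 1 DLT among 6 participants is 1 − (1 − p)^6:
- 1 − 0.9^6 = 0.469
- 1 − 0.8^6 = 0.738
- 1 − 0.7^6 = 0.882

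This is the chance that any DLT occurs. The chance that someone is affected by the conflict is lower, because Section 6 ends treatment after some DLTs anyway.

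**The case against.** The best defence is that the operative text already settles the matter. Section 5.6 makes Section 5.4 the removal list, Section 5.4 limits the criterion to DLTs requiring discontinuation, and Section 6 gives the detail. On that view the phrase in the synopsis and Section 12.4 is loose summary wording. The first part stands: the sections read together favour continuing. Under the Section 5.2 definition, an unconditional stop would also leave the Cycle 1 reduction permission and the 14-day rule with little to do for related toxicity.

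It does not remove the opposite instruction. Neither Section 12.4 nor the synopsis carries the qualifier, and Section 5.2, to which Section 5.4 refers for it, does not supply it. The Section 6.0 proviso defers to Section 5.4, which itself permits Cycle 1 reductions. The Table 6-1 note excepting Cycle 1 concerns only toxicity of lower grade than the table specifies.

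A reader might also infer that Section 11.1.1 removes everyone stopped early for toxicity and so always inflates the response rate. The documents do not support that. Section 11.1.1 keeps participants with objective progression before the end of Cycle 1, and Kaposi sarcoma is assessed under Section 11.2. The direction is not fixed either: with no responders, 0/4 and 0/3 are both 0%; if one of two excluded participants had responded, 3/12 = 25% becomes 2/10 = 20%.

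**Conclusion.** The contradiction is real, sits in current text, and should be corrected. It concerns who stays on treatment after a Cycle 1 DLT and the data they can then contribute. It does not alter DLT counting or the MTD under Sections 5.2 and 12.1, because the DLT is already recorded when the stopping question arises. The synopsis definition is a separate defect: applying it could change whether an 8-13 day hold, or some Grade 4 neutropenia, counts as a DLT.

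No document-based count of affected participants is available. A reader might take the ceiling of 1 DLT in 6 at a declared MTD as the DLT rate; that gives 1 − (5/6)^6 = 67% for 6 participants and 1 − (5/6)^12 = 89% for 12. But 1/6 is the largest observed proportion the rule tolerates, not a stated rate, so those figures rest on an assumption.

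The conclusion assumes that the phrase in Section 12.4 and the synopsis means what it says without a qualifier. The direction of the fix assumes that Sections 5.4 and 6 express the intended rule. If the sponsor intends the reverse, those sections must change instead.

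**What to change.** 1. In the synopsis and Section 12.4, replace "unacceptable toxicity (including DLT in cycle 1" (with its closing parenthesis) by *any criterion in Section 5.4*.
2. In Section 5.4, replace the DLT bullet with: *A Cycle 1 DLT for which Section 6 directs permanent discontinuation, subject to the clinical-benefit exceptions with Study Chair approval stated there; other participants with a Cycle 1 DLT may resume at the dose Section 6 directs if no other Section 5.4 criterion applies.*
3. In the 14-day bullet of Section 5.4, delete the parenthesis calling it the Section 5.2 DLT definition. The 14-day stopping rule itself stays.
4. Align the synopsis DLT definition with Sections 5.2 and 12.1: a delay of more than 7 days, and Grade 4 neutropenia of any duration.

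Optionally, add a supporting response rate over all treated participants with measurable disease, using any response actually observed and counting those without a post-baseline assessment as non-responders. Participants who stop for a Cycle 1 DLT should not be coded as non-responders by rule, since the off-treatment scan may show a response.

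The cost is amendment wording in the synopsis and Sections 5.4 and 12.4, plus one extra tabulation if the optional item is taken. No procedures or participants are added.

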## 6.0 DOSING DELAYS/DOSE MODIFICATIONS

### Dose modifications for Cabozantinib (XL184)

Toxicities warranting treatment delays and dose modifications, along with supportive care guidelines, are noted below.

Stratum-based dose de-escalation of cabozantinib will be permitted for participants experiencing specified toxicity when treated at a particular dose level, as noted below; reductions will be at one-dose-level increments. In no case will dose de-escalation occur beyond the lowest specified Dose Level dose for a particular Stratum (Dose Level -1 for Stratum A; Dose Level -2 for Stratum B and Stratum C). Dose reductions are permanent. No intra-participant dose escalation will be permitted.

**NOTE: Dose modification during Cycle 1 WILL be permitted.** Participants will be permitted to continue study therapy provided no other criteria for protocol discontinuation apply ([Section 5.4](#)). **HOWEVER, treatment delay of 14 days or longer due to unresolved toxicity during Cycle 1 will require discontinuation of study treatment** ([Section 5.4](#)).

**NOTE:** If a participant experiences several adverse events and there are conflicting recommendations, the investigator should use the recommended dose adjustment that reduces the dose to the lowest level.

**NOTE:** Starting in Cycle 2, if toxicity requiring treatment delay does not resolve in less than or equal to 6 weeks, the study treatment will be discontinued. Treatment delays for other reasons may be permitted at the discretion of the Study Chairs.

Dose De-Escalation Schedule			
Dose Level	Dose of Cabozantinib (XL184)*		
	Stratum A ART Regimens Including Drugs that Inhibit CYP3A4 A (mg/day)	Stratum B ART Regimens Including Drugs that Induce CYP3A4 B (mg/day)	Stratum C All Other ART Regimens C (mg/day)
Level -2	-	20	20
Level -1	20 mg every other day	40	40
Level 1	20	60	60
Level 2	40	100	-
Level 3	60	-	-

\* Cabozantinib (XL184) must be taken whole and on an empty stomach. Participants must fast for 2 hours before and 1 hour following each dose of cabozantinib (XL184). To permit pharmacokinetic sampling studies, AM dosing is required during the first cycle of therapy.

AStratum A: Participants taking either ritonavir-boosted or cobicistat-boosted ART regimens

BStratum B: Participants taking either efavirenz or etravirine-based ART regimens.

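### Whether a Cycle 1 DLT ends study treatment is stated both ways: the Synopsis and 12.4 stop every such participant, while 5.4, 6.0 and Tables 6-1 and 6-2 let some continue at a reduced dose

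*Combined protocol and SAP*

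**What the plan says.** **Stopping rule.** The Synopsis, under Duration, states: "Treatment may continue indefinitely until one of the following criteria applies: 1) unacceptable toxicity (including DLT in cycle 1". Section 12.4 repeats it: "1) unacceptable toxicity (including DLT in cycle 1". Neither place limits the rule to particular DLTs.

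**What counts as a DLT.** The Synopsis closes its definition with "dose reduction required during Cycle 1 due to a cabozantinib-related adverse event will be considered a DLT", and Section 12.1 says the same. Section 5.2 goes further: "dose reduction required during Cycle 1 due to a cabozantinib-related adverse event (including for intolerable cabozantinib-related grade 2 non-hematological toxicity".

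**Permission to continue.** Section 5.4 ends treatment only for a DLT that calls for discontinuation, and refers to 5.2 for what that means. It then adds: "Dose reductions in the first cycle of therapy for cabozantinib-related adverse events are permitted". Section 6.0 says in bold "Dose modification during Cycle 1 WILL be permitted", and lets such participants stay on therapy if no other stopping criterion in 5.4 is met. Tables 6-1 and 6-2 give hold-then-resume instructions at one dose level lower for several events that are DLTs when they occur in Cycle 1.

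**Delays.** Sections 5.2 and 12.1 make a Cycle 1 toxicity delay of more than 7 days a DLT. Sections 5.4 and 6.0 end treatment at 14 days or more, and 5.4 cites 5.2 as the source of that figure.

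**The concern.** Read together, the DLT definition and the stopping rule in the Synopsis and 12.4 end treatment for anyone whose dose is reduced in Cycle 1 for a related event. Sections 5.4 and 6.0 give the opposite answer for the same person. The wording in 5.4 does not bridge the gap. It implies that some DLTs do not require stopping, which the Synopsis and 12.4 do not allow, and it sends the reader to 5.2, which does not say which DLTs those are.

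At stake is follow-up that differs by site practice, and only in participants who had toxicity:

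- **Later-cycle safety.** Exposure after Cycle 1 bears on the primary objective of safety and tolerability.
- **Response.** Section 11.1.1 requires a minimum of one treatment cycle plus a repeat disease assessment, with early objective progression excepted. A participant stopped in Cycle 1 may therefore not be evaluable.
- **PK.** Full steady-state sampling falls on Days 22/23. Section 10.1.1 provides for rescheduling after a missed dose if the participant is staying on treatment.
- **CD4, CD8 and viral load.** The number of on-treatment samples entering the repeated-measures analysis in 12.4 depends on how long treatment lasts.

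**Working it through.** The plan gives no figure to reproduce, so the check applies each rule to the same case.

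| Cycle 1 event | Is it a DLT? | Synopsis / 12.4 | 5.4, 6.0, Tables 6-1 and 6-2 |
|---|---|---|---|
| Dose reduction for a related event | Yes (Synopsis, 5.2, 12.1) | Treatment ends | May continue at the reduced dose |
| Related grade 3 non-hematologic event despite optimal prophylaxis | Yes (all three) | Treatment ends | Table 6-1: hold, then resume one level lower |
| Grade 4 neutropenia | Yes, any duration (5.2, 12.1) | Treatment ends under 12.4 | Table 6-2: hold, then resume one level lower |
| Toxicity delay of 8 to 13 days | Yes (5.2, 12.1) | Treatment ends under 12.4 | Delay alone does not end treatment |
| Toxicity delay of 14 days or more | Yes (all three) | Treatment ends | Treatment ends |
| Related grade 4 non-hematologic event | Yes (all three) | Treatment ends | Table 6-1: ends, unless clear benefit and Study Chair approval |

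The first four rows conflict. The fifth does not, and the sixth mostly does not.

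Two details confirm that the conflict lies within Cycle 1. The closing note to Table 6-1 excludes the first cycle only from discretionary changes for lower-grade toxicity, so its graded instructions do apply in Cycle 1. And the 14-day figure that 5.4 attributes to 5.2 is not in 5.2. It appears in the Synopsis definition, whose delay and neutropenia criteria differ from those in 5.2 and 12.1.

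**Size.** The documents state no expected DLT rate. I assume 1/6 to 2/6 and apply it to the enrollment range in 12.2, which is 16 to 42:

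- 16 × 1/6 = 2.7 and 16 × 2/6 = 5.3, or about 3 to 5 participants.
- 42 × 1/6 = 7 and 42 × 2/6 = 14 participants.

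These are upper bounds, because they count every DLT, including those in the last two rows.

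**Response illustration.** Section 12.4 reports response for any malignancy with at least 4 enrolled. Suppose 4 are enrolled, 1 responds, and the denominator is evaluable participants (12.4 does not say which denominator it uses). The rate is 1/4 = 25%. If one non-responder is stopped in Cycle 1 and becomes non-evaluable, it is 1/3 = 33%.

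**The case against.** The strongest reply is that the operative treatment sections agree with each other. Section 5.6 sends sites to 5.4 for removal criteria, and 6.0 addresses this very case in bold. The other side is a synopsis line and one sentence in an analysis section. This stands in part: it means sites may diverge, not that they will. It does not remove the contradiction. The text supplied contains no rule of precedence among sections, the Synopsis is part of the protocol, and the parenthesis expressly places Cycle 1 DLTs within unacceptable toxicity, so that phrase leaves no discretion.

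A second reply is that the consequences are partly covered elsewhere, and this also stands in part. CD4, CD8 and viral load are collected at treatment discontinuation (9.3). PK can be rescheduled or waived, and a sample is requested at the time of a DLT (5.2, 10.1.1). An interruption for toxicity disturbs the PK schedule under either rule. All treated participants are evaluable for toxicity (11.1.1), and those removed for unacceptable events are followed to resolution or stabilization (5.5). What remains is a difference in the length of on-treatment follow-up and in who becomes response-evaluable.

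A third reply is that Section 6 already sets out, largely by event and grade, what permits resumption and what requires stopping. That is correct, and a separate new list of DLTs is not needed.

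**Conclusion.** The inconsistency is real and lies between current sections. A participant whose dose is reduced in Cycle 1 for a related event must stop under the Synopsis and 12.4 and may continue under 5.4 and 6.0. A toxicity delay of 8 to 13 days meets the same split between 12.1 with 12.4 and 5.4 with 6.0.

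A reader might infer two stronger things that the documents do not support:

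- **That the MTD is compromised.** It is not, by this conflict. The event is counted as a DLT whether or not treatment continues, and 5.2 treats a participant with a DLT as evaluable for escalation. The difference between the Synopsis and 5.2 over which events qualify as DLTs is a separate matter.
- **That 7 to 14 participants are certain to be affected.** That range assumes DLT rates of 1/6 to 2/6, takes the maximum enrollment of 42, and includes DLTs that stop treatment under either reading. At 16 enrolled the ceiling is about 3 to 5. The true number is lower in both cases and cannot be derived from the documents.

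The effect therefore falls on later-cycle safety exposure and the secondary endpoints, selectively in participants with toxicity. The contradiction itself does not depend on the assumed rates.

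**What to change.** Reconcile the Synopsis, 5.2, 5.4, 6.0, 12.1 and 12.4 to one rule. Which rule applies is a clinical decision for the sponsor, and this review takes no position on it.

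1. State separately whether an event counts as a DLT for escalation and whether it requires discontinuation. Make the second statement by cross-reference to the Section 6 tables, aligned with whichever rule is chosen.
2. Correct the two references from 5.4 to 5.2: the one for DLTs that require stopping, which 5.2 does not identify, and the one for the 14-day delay, which 5.2 does not contain.
3. Optionally, flag participants who continue after a DLT and report their later-cycle data by dose received. This helps interpretation but is not needed to resolve the contradiction.

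The cost is protocol wording in an amendment and, if the option is taken, one analysis flag. Sample size and escalation rules are unaffected.
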